Treatment-emergent adverse events: Table 1 summarizes adverse events, regardless of relationship, to infigratinib as a single agent at the maximum tolerated dose of 125 mg, 3 weeks on, 1 week off (N = 433 subjects), and Table 2 summarizes Grade 3 to 4 adverse events. The on-target effects on calcium-phosphorus homeostasis result in the observed increases in calcium (13.4% any grade, 3.2% Grade 3-4), phosphorus (61.2% any grade, 6.7% Grade 3 to 4), and creatinine (23.8% any grade). These are not associated with clinical symptoms and in general have been mild to moderate in severity, manageable, and reversible. Guidelines for management of on-target hyperphosphatemia have been implemented.

Ocular adverse events (corneal or retinal) occur in about 50% of subjects, but in general are mild to moderate in severity and reversible: for example, Grade 1 to 2 dry eye was reported in 21.5% and Grade 1 to 2 blurry vision in 9.9%. Grade 3 ocular events occurred in 3% of subjects; no Grade 4 ocular events have been reported. Grade 3 adverse events of cataract (N = 3, 0.7%), visual impairment (N = 2, 0.5%), and keratitis (N = 2, 0.5%) were the events that

occurred in more than one subject; others were reported once. Adverse events of blurred vision, visual impairment, and keratitis led to study drug discontinuation for N = 2, 0.5% subjects each. Since the cornea and retina were identified from preclinical safety studies as a potential target organ of interest, protocol-mandated ophthalmologic examinations have been performed routinely and frequently throughout studies.

Subjects have been monitored for potential QT prolongation: N = 3 (0.7%) of subjects have had a new QTc value > 500 msec, N = 4 (1.0%) have had a QTcF change of > 60 msec, and N = 63 (15.0%) have had a QTcF change > 30 and  $\leq$  60 msec. None of these events was considered serious nor led to treatment withdrawal or dose reduction/interruption. Subjects have also been monitored for potential decrease in ventricular ejection fraction by echocardiogram or multi-gated acquisition. N = 6 (1.4%) of subjects had a Grade 2 abnormality (no Grade 3-4 events), which did not lead to study drug discontinuation.

Other notable adverse events include stomatitis (34.9%) and alopecia (26.8%).

**Table 1:** Adverse events occurring in ≥ 10% of adult oncology subjects treated with infigratinib monotherapy

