# 4.1 General Concomitant Medication and Supportive Care Guidelines

#### 4.1.1 Concomitant Medication

Administration of other anticancer therapies within 2 weeks of enrollment, except ongoing administration of a bisphosphonate drug or denosumab as treatment for bone metastasis or ongoing administration of a luteinizing hormone-releasing hormone agonist (such as goserelin acetate or leuprolide acetate) or other endocrine therapy, is prohibited.

Palliative radiotherapy on study is permitted for the treatment of painful bony lesions providing the lesions were known at the time of study entry and the investigator clearly indicates that the need for palliative radiotherapy is not indicative of disease progression. In view of the current lack of data about the interaction of infigratinib with radiotherapy, infigratinib treatment should be interrupted during palliative radiotherapy, resuming infigratinib treatment after recovery to ≤ Grade 1 radiotherapy-related toxicity.

Details for specific medications prohibited while on study are provided in Appendix A. The rationale for the restricted medications is provided below.

Strong inhibitors of CYP3A4 such as the ones listed in Appendix A are prohibited because infigratinib is a likely substrate of this isoenzyme.

Strong inducers of CYP3A4 are prohibited because their usage may decrease the exposure of infigratinib. Therefore, agents such as those listed in Appendix A are prohibited. Please note that the list may not be exhaustive.

Subjects must also avoid the consumption of grapefruits; grapefruit juice; grapefruit hybrids; pomegranates; star fruits; pomelos; Seville oranges; or juice within 7 days prior to the first dose of infigratinib and throughout the treatment period due to a potential CYP3A4 interaction with study drug.

Medications that increase the serum levels of phosphorus and/or calcium are prohibited.

Preliminary clinical data have shown that infigratinib has no effect on cardiac conduction or ECG intervals (See current version of the infigratinib Investigator's Brochure). However, medications that are known to prolong the QT/QTc interval or induce TdP (risk of TdP/QT prolongation) are prohibited. List of these medications is given in Appendix A. Please note that the list might not be comprehensive.

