# 9. STUDY CALENDAR

	Screening	On Treatment (1 Cycle = 28 days)						Post-Treatment			
2	(Within	Cycle 1			Cycle 2		Cycles ≥ 3	End of Treatment /	30-day		
	21 days of Cycle 1, Day 0)	Day 1 (± 3 days)	Day 4 (± 1 day)	Day 15 (± 3 days)	Day 1 (± 3 days)	Day 15 (± 3 days)	Day 1 (± 3 days)	withdrawal (0 to 14 days from decision to discontinue) 	Follow-up Safety Visit (+ 7 days)  F	Other Follow-up 	
Informed Consent 	Х										
Medical/Tumor History 	х										
Physical Examination (within 24 hours prior to start of each cycle) 	x	х		x	х		x	X	x	( X )	
ECOG Performance Status 	х	х		Х	Х		Х	Х	Х	( X )	
Safety Labs/Measurements	5										
Vital Signs (within 24 hours prior to start of each cycle) 	х	х		х	х		х	х	х	( X )	
Hematology (CBC, differential, platelets) 	х	х		х	х	Х	х	х		( X )	
Complete metabolic panel 7	Х	х	Х	Х	Х	Х	X	Х		(X)	
Amylase, lipase 	х	Х		Х	Х	Х	Х	х		( X )	
Calcium, magnesium, phosphorus 	х	х	х	х	х	Х	x	х		( X )	
Urinalysis 10	Х										
Pregnancy Test 11	х	Х						х			
Electrocardiogram 12	х				х		C4D1, C6D1 (± 7 days) then every 6 cycles (all ± 14 days)	х			
Transthoracic echocardiogram	х				х			х			
Ophthalmology evaluation 	х				X ± 7 da ys		C3D1, C4D1, C6D1 (± 7 days), then every 3 cycles (± 14 days)	х			

IRB-53650 Version 11 Page 52 of 72 11 November 2021

Hormone Receptor-positive, HER2-negative, FGFR-altered Advanced Breast Cancer

	Screening			On Tre	eatment (	Post-Treatment				
	(Within	Cycle 1		Сус	ele 2	Cycles ≥ 3	End of Treatment /	30-day		
Protocol Activity	21 days of Cycle 1, Day 0)	Day 1 (± 3 days)	Day 4 (± 1 day)	Day 15 (± 3 days)	Day 1 (± 3 days)	Day 15 (± 3 days)	Day 1 (± 3 days)	withdrawal (0 to 14 days from decision to discontinue) 	Follow-up Safety Visit (+ 7 days)  Fol	
Registration 	≤ 7 days bef Cycle 1, Day 1									
Treatment										
Infigratinib administration 			1 week off			3 weeks on / 1 week off 3 weeks on / 1 week off				
Cohort 1: Tamoxifen administration 			Continuous		Continuous		Continuous			
Tumor Assessment										
CT (chest, abdomen, pelvis) 	х						C3D1 (+7 days), then every 2 cycle (± 7 days)	( X )		
Plasma collection 		х		х				Х		
Research tumor biopsy 19	Х			х						
Tumor sequencing 	Х									

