- 12. Electrocardiogram: 12-lead ECG to be performed during Screening, at Cycle 2 Day 1 (± 3 days), Cycle 4 Day 1 (± 7 days), Cycle 6 Day 1 (± 7 days), and then every 6 cycles (± 14 days), and at End-of-Treatment. Additional assessments should be conducted as clinically indicated.
- 13. Echocardiogram: Transthoracic echocardiogram to be performed during Screening, at Cycle 2 Day 1 (± 3 days), and at End-of-Treatment. Additional assessments should be conducted as clinically indicated.
- **14. Ophthalmology evaluation:** Ophthalmologic examination will be performed by an ophthalmologist during Screening, on Day 1 (± 7 days) of Cycles 2, 3, 4 and 6; then every 3 cycles (± 14 days); and at End-of-Treatment, as well as urgently with any new onset of visual symptoms. These assessments will include visual acuity testing, slit lamp examination of the anterior eye segment, intraocular pressure, dilated fundoscopy, and retinal optical coherence tomography (OCT). Additional examinations such as specular microscopy (that enables a magnified, direct view of the corneal epithelium) and corneal pachymetry will be performed as clinically indicated.
- **15. Infigratinib Administration:** One cycle of infigratinib will be provided to subjects at the beginning of each cycle. Starting dose level of infigratinib for individual subjects will be as defined by study protocol, and may be either 125 mg; 100 mg; or 75 mg infigratinib, each dose level administered as 3 weeks on, 1 week off for every 28-day cycle.
- **16. Tamoxifen Administration:** In Cohort 1, tamoxifen will be prescribed to subjects and will be started at 4 to 8 hours after the administration of infigratinib, starting on Cycle 1 Day 1. Dose is tamoxifen 20 mg/day by mouth continuously.

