#### 10. MEASUREMENTS

### 10.1 Primary endpoint:

The primary endpoint is the incidence of dose-limiting toxicities (DLTs) in the first 2 cycles of therapy at a specific dose. In Cohort 1, in a subset of subjects who start at infigratinib 100 mg and complete 2 cycles with no DLTs and who remain on study for Cycles 3 and 4, the dose of infigratinib will be increased to 125 mg starting with Cycle 3 and the number of DLTs in Cycles 3 and 4 will be counted toward the primary endpoint (for the 125 mg dose), in addition to the number of DLTs in Cycles 1 and 2 (for the 100 mg dose). For all other subjects, the primary endpoint will be the number of DLTs in Cycles 1 and 2.

DLTs will be graded using NCI CTCAE (Common Terminology Criteria for Adverse Events), v5.0. DLTs will be defined as an adverse event (AE) or abnormal laboratory value at least possibly related to therapy with infigratinib including those AEs and abnormal laboratory values that result in a failure to meet the criteria for re-treatment. The criteria for defining a DLT, which are pre-specified based on the pre-clinical toxicity of infigratinib, are listed in Table 7.

Individual subjects who had a DLT may be retreated, after recovery, at the next lowest dose level.

Investigators will notify QED Therapeutics within 7 days of any DLTs observed.

**Table 7.** Criteria for defining dose-limiting toxicities

TOXICITY	DLT CRITERION
Skipped/ delayed dose	The inability to administer infigratinib on ≥ 75% of scheduled treatment days during cycle 1 at that dose (ie, ≥ 16 days of the 21 days of planned treatment) due to unresolved adverse event of any grade and considered at least possibly, probably, or definitely related to the study drug.
	Delay in 2 nd cycle administration at that dose due to failure of recovery from a possibly, probably, or definitely related adverse event to Grade ≤ 1 or baseline by Day 43 (Day 28 of Cycle 1 + 15 days), except for alopecia.
Blood/ bone marrow	Neutropenia     • Febrile, CTCAE Grade ≥ 3.     • CTCAE Grade ≥ 3 for > 7 consecutive days
	Thrombocytopenia
	Anemia CTCAE Grade 4
Renal/ genitourinary	Creatinine:  • CTCAE Grade 1 for > 7 consecutive days and serum inorganic phosphorus  > 5.5 mg/dL and/or serum total calcium x serum inorganic phosphorus  > 55 mg²/dL² and despite phosphorus lowering therapy for ≥ 14 days
	
 
CTCAE Grade 2 for > 7 consecutive days
 
CTCAE Grade ≥ 3
 

**Table 7.** Criteria for defining dose-limiting toxicities

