TOXICITY	DLT CRITERION	
Hepatic	Bilirubin: • CTCAE Grade 2 for > 7 consecutive days	
	• CTCAE Grade ≥ 3	
	AST or ALT: • Grade 3 for > 7 consecutive days • CTCAE Grade 4	
	Hy's Law	
	
 
ALT or AST ≥ 3 x upper limit of normal (ULN)
 
AND
 
Serum total bilirubin > 2 x ULN
 
	
	For patients with known hepatic metastases:  • AST or ALT > 8 x ULN  OR	
	• AST or ALT > 5 x ULN for ≥ 14 days	
Pancreas	Pancreatitis CTCAE Grade ≥ 2	
	Amylase/lipase (serum-high): CTCAE Grade ≥ 3 asymptomatic amylase and/or asymptomatic lipase not reversible to CTCAE Grade ≤ 2 within 7 days	
Cardiac	QTcF interval > 500ms	
	Other cardiac CTCAE Grade ≥ 3	
Constitutional	Fatigue CTCAE Grade 3 for > 7 consecutive days	
	Fatigue CTCAE Grade 4	
Ocular/visual	Any ocular/visual toxicity CTCAE Grade ≥ 3.	
Gastrointestinal	CTCAE Grade 3 or 4 nausea/vomiting and/or diarrhea despite the use anti-emetic and anti-diarrhea therapy, respectively	
Metabolic/ laboratory	
 
Hyperphosphatemia (serum-high):
 
Serum inorganic phosphorus > 7.0 mg/dL for > 7 consecutive days despite phosphorus-lowering therapy for at least 14 days.
 
Serum inorganic phosphorus > 9.0 mg/dL, despite phosphorus-lowering therapy for at least 14 days.
 
Serum inorganic phosphorus > 10.0 mg/dL
 
Hypercalcemia (serum-high)
 
Serum calcium CTCAE Grade 2 for > 7 consecutive days.
 
Serum calcium CTCAE Grade ≥ 3.
 
	
Other	Any death not clearly due to the underlying disease or known, extraneous causes.	
	Clinical evidence for any grade (CTCAE Grade ≥ 1) of ectopic, de-novo -calcification within the soft tissue including the peri-articular spaces and vascular as well as visceral tissues (eg, kidney, lung, stomach, myocardium, etc.)	
	
 
Any other CTCAE Grade 3 or 4 non-hematological toxicity except with following exclusions:
 
• Alkaline phosphatase CTCAE Grade ≥ 3.
 
• Lymphocytopenia CTCAE Grade ≥ 3 unless considered clinically significant.
 
	

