APPENDIX B: List of drugs to be used with caution while on study

Category	Drug Names		
CYP3A substrates with narrow therapeutic index	alfentanil, cyclosporine, diergotamine, dihydroergotamine, ergotamine, fentanyl, sirolimus, tacrolimus, terfenadine, warfarin sodium or any other coumadin-derivative anticoagulants, direct thrombin inhibitors (eg, argatroban), and Factor Xa inhibitors (eg, rivaroxaban)		
Moderate inhibitors of CYP3A4	amprenavir, aprepitant, atazanavir, cannabinoids, casopitant, cimetidine, ciprofloxacin, darunavir, diltiazem, fosamprenavir, imatinib, metronidazole, Schisandra sphenanthera, sertraline, suboxone, tofisopam, verapamil, zafirlukast		
Moderate inducers of CYP3A4	bosentan, cotrimoxazole, efavirenz, etravirine, ethosuximide, genistein, metyrapone, mexiletine, modafinil, nafcillin, talviraline, tipranavir		
Medications which alter the pH of the GI tract a,b	antacids, H₂antagonists (eg, ranitidine), proton-pump inhibitors (eg, omeprazole)		
Medications that have possible risk of TdP/QT prolongation	alfuzosin, amantadine, atazanavir, chloral hydrate, clozapine, dolasetron, eribulin, famotidine, felbamate, fingolimod, foscarnet, fosphenytoin, gatifloxacin, gemifloxacin, granisertron, iloperidone, indapamide, isradipine, lapatinib, lithium, moexipril, nicardipine, nilotinib, octreotide, ofloxacin, ondansetron, oxytocin, paliperidone, pasireotide, quetiapine, ranolazine, risperidone, roxithromycin, sertindole, sunitinib, tamoxifen, tizanidine, vardenafil, venlafaxine, ziprasidone		
Medications that have conditional risk of TdP/QT prolongation	amitriptyline, amisulpride, ciprofloxacin, clomipramine, desipramine, diphenhydramine, doxepin, fluoxetine, galantamine, imipramine, nortriptyline, paroxetine, protriptyline, sertraline, solifenacin, trazodone, trimethoprim-sulfa, trimipramine		
BCRP substrates	atorvastatin, irinotecan, methotrexate, rosuvastatin, simvastatin, sulfasalazine, topotecan		

Abbreviations: BCRP, breast cancer resistance protein; CYP, cytochrome p; F DA, Food and Drug Administration; GI, gastrointestinal; TdP, Torsades de Pointes

<sup>a Infigratinib should be dosed at least 2 hours before or 10 hours after dosing with a gastric protection agent.

b If possible, proton pump inhibitors should be avoided due to their long pharmacodynamic effect and replaced with H2 antagonists or antacids.

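### QTcF above 500 ms is a DLT, yet the one fixed-time ECG in each DLT window nominally follows the drug-free week, and none is required once infigratinib has accumulated

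*Combined protocol and SAP*

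**What the plan says.** Section 10.1 defines the endpoint: "The primary endpoint is the incidence of dose-limiting toxicities (DLTs) in the first 2 cycles of therapy at a specific dose". For subjects who start at 100 mg and are escalated, the dose is "increased to 125 mg starting with Cycle 3 and the number of DLTs in Cycles 3 and 4 will be counted" toward the 125 mg level. Each subject therefore has a Cycles 1-2 window, and escalated subjects also have a Cycles 3-4 window. Table 7 lists under Cardiac "QTcF interval > 500ms".

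Infigratinib is taken on Days 1-21 of a 28-day cycle (Section 4), with Days 22-28 off (Section 4.1.2, hyperphosphatemia). Tamoxifen is continuous.

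Section 9, footnote 12 gives the ECG times: "12-lead ECG to be performed during Screening, at Cycle 2 Day 1 (± 3 days), Cycle 4 Day 1 (± 7 days", then Cycle 6, every 6 cycles thereafter, and End of Treatment. The calendar row agrees; its later-cycle entry reads "C4D1, C6D1 (± 7 days) then every 6 cycles (all ± 14 days". There is no ECG at C1D1, C1D4, C1D15, C2D15 or C3D1. Further ECGs are done when clinically indicated. Table 6 adds repeat ECGs, but only after a prolonged QTcF has been found.

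On background risk, Section 2.2.9 reports that "N = 3 (0.7%) of subjects have had a new QTc value > 500 msec", with a QTcF change above 60 msec in 4 subjects (1.0%) and above 30 up to 60 msec in 63 (15.0%). Appendix B names tamoxifen among drugs with possible QT risk ("sertindole, sunitinib, tamoxifen, tizanidine"). Section 4.1.1 states, twice, "Preliminary clinical data have shown that infigratinib has no effect on cardiac conduction or ECG intervals".

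**The concern.** The QTcF criterion is an instrument reading. Unless the subject has symptoms, the trial learns of it only from a scheduled ECG, so the schedule decides whether this part of the primary endpoint can be observed. A nominal Day 1 ECG follows a week without infigratinib. Tamoxifen is still on board, so it is infigratinib's contribution, and hence the combination at working exposure, that is under-observed.

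Two things are at stake. A missed QTcF event lowers the DLT count at that dose, and it leaves the QTcF actions in Table 6 untriggered for that subject. The protocol itself treats exposure at the time of the reading as relevant: for a QTcF above 500 msec, Table 6 asks for a plasma infigratinib concentration.

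The gap is widest around escalation. A subject moves to 125 mg at nominal Day 57 with no scheduled ECG since nominal Day 29. The next is nominally Day 85, after all Cycle 3 dosing.

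**Working it through.** The plan gives no figure for this point, so there is nothing to reproduce. The check has four steps.

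**Inputs.** Dosing days (Sections 4 and 4.1.2), ECG days (Section 9, footnote 12) and DLT windows (Section 10.1). Mean accumulation ratio R of 3 to 8 with daily dosing at 60 mg or more (Section 2.2.3). Prior rate of 0.7% for QTc above 500 msec (Section 2.2.9). A linear one-compartment model with immediate absorption and constant dose is my assumption.

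**1. Calendar.**
- C2D1 is Day 29 and the last Cycle 1 dose is Day 21: 29 − 21 = 8 days = 192 h.
- C4D1 is Day 85 and the last Cycle 3 dose is Day 77: again 8 days.
- The C2D1 ± 3 window runs from C1D26 to C2D4: 7 days, of which 3 are off drug and 4 are dosing days.
- The C4D1 ± 7 window runs from C3D22 to C4D8: 15 days, of which 7 are off drug and 8 are dosing days.
- Neither window contains any of Days 15-21 of a cycle.

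**2. Level remaining.** If a fraction f is left after 24 h, then R = 1/(1 − f), so f = 1 − 1/R.
- R = 3: f = 0.667, effective half-life 24 × ln 2 / −ln f = 41.0 h.
- R = 8: f = 0.875, effective half-life 124.6 h.

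The share of the Day 21 peak left before dosing on Day 29 is f^8: 0.667^8 = 0.039 and 0.875^8 = 0.344. Adding up daily doses in the same way gives, as a share of the Day 21 peak:

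| Time | R = 3 | R = 8 |
|---|---|---|
| C1D15, pre-dose | 66% | 79% |
| C1D26 (early edge of window) | 13% | 51% |
| C2D1, pre-dose | 4% | 34% |
| C2D1, just after dose | 37% | 48% |
| C2D4, pre-dose (late edge) | 48% | 54% |
| C3D22 (early edge of window) | 67% | 90% |
| C4D1, pre-dose | 4% | 35% |
| C4D8, pre-dose (late edge) | 63% | 70% |

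A pre-dose ECG on the nominal day is the low point of the cycle in both cases.

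**3. Expected yield.** The chance of at least one event is 1 − (1 − 0.007)^n. For n = 6 this is 4.1%, and for n = 12 it is 8.1%.

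**4. Effect on the decision.** Under Section 12.4, no DLT in 3 subjects declares a dose safe, while one DLT adds 3 subjects. One unseen event among the first 3 is enough to change the path.

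**The case against.** The strongest reply has four parts.

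*The windows and Day 1 itself allow on-drug ECGs.* This is right. Day 1 is a dosing day, and footnote 12 does not say the ECG precedes the dose; the pre-dosing instruction appears in the hematology footnote. A reader might infer that no on-drug ECG is planned at all, but the documents do not support that. More than half of the days in each window are dosing days, and C3D22 is only about 24 h after the last dose. What stands is that none of these higher-exposure times is required.

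*The drug is not gone by Day 1.* A reader might take the Day 1 half-life of 3 to 7 h (Section 2.2.3), divide it into 192 h to get 27 to 64 half-lives, and conclude that essentially no drug remains. That does not fit the same section: a 7 h half-life with daily dosing implies accumulation of about 1.1, not 3 to 8. Only the 4% to 34% range is compatible. At the upper end, the claim that the ECG reflects tamoxifen alone is not established.

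*The risk is small and guarded.* Section 2.2.9 adds that none of the QT events was serious or changed treatment. A 30 to 60 msec change is not the DLT criterion. Entry is barred at QTcF above 470 msec, drugs with established QT risk are prohibited, and clinically indicated ECGs are allowed. This limits the size of the point. It does not supply a required ECG at accumulated exposure, and the 0.7% is a monotherapy rate; the documents give none for the combination.

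*The no-effect sentence cites the Investigator's Brochure*, which is not among the documents. Uncontrolled outlier counts do not disprove it. The most that can be said is that the two sections need reconciling.

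**Conclusion.** The point holds as one of detection. Each DLT window has a single fixed-time ECG, nominally 8 days after the last infigratinib dose and with timing relative to that day's dose unstated. No ECG is required while infigratinib has accumulated. If it is taken before dosing on the nominal day, about 4% to 34% of the on-treatment level remains. That range rests on the one-compartment assumption and on the stated accumulation ratios.

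An asymptomatic QTcF DLT could be missed; the documents do not show that it would be. The expected yield is modest (4.1% in 6 subjects, 8.1% in 12, at the monotherapy rate). Because one event can redirect a 3+3 decision and the correction is cheap, it is worth making. It does not call the design as a whole into question.

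**What to change.** Reconcile footnote 12 with the Table 7 QTcF criterion. Require the one scheduled ECG in each DLT window to be taken on a dosing day after repeated dosing, and record its time relative to that day's dose.

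- **Cycles 1-2:** the existing C1D15 or C2D15 visit can carry the ECG in place of C2D1. Both have a ± 3 day window, so every permitted day (Days 12-18) is a dosing day. No ECG is added.
- **Cycles 3-4 after escalation:** the sponsor should restrict the C4D1 window or choose another on-drug day.
- **Text:** reconcile the two no-effect sentences in Section 4.1.1 with the QTc figures in Section 2.2.9.

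The cost is a calendar and footnote amendment, and possibly one short extra trip in Cycles 3-4. Giving up the C2D1 reading also has a price. Moving it to C1D15 leaves no scheduled ECG in Cycle 2. Moving it to C2D15 delays the first on-treatment ECG from nominal Day 29 to Day 43. The sponsor should weigh these and state the choice.

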#### 10. MEASUREMENTS

### 10.1 Primary endpoint:

The primary endpoint is the incidence of dose-limiting toxicities (DLTs) in the first 2 cycles of therapy at a specific dose. In Cohort 1, in a subset of subjects who start at infigratinib 100 mg and complete 2 cycles with no DLTs and who remain on study for Cycles 3 and 4, the dose of infigratinib will be increased to 125 mg starting with Cycle 3 and the number of DLTs in Cycles 3 and 4 will be counted toward the primary endpoint (for the 125 mg dose), in addition to the number of DLTs in Cycles 1 and 2 (for the 100 mg dose). For all other subjects, the primary endpoint will be the number of DLTs in Cycles 1 and 2.

DLTs will be graded using NCI CTCAE (Common Terminology Criteria for Adverse Events), v5.0. DLTs will be defined as an adverse event (AE) or abnormal laboratory value at least possibly related to therapy with infigratinib including those AEs and abnormal laboratory values that result in a failure to meet the criteria for re-treatment. The criteria for defining a DLT, which are pre-specified based on the pre-clinical toxicity of infigratinib, are listed in Table 7.

Individual subjects who had a DLT may be retreated, after recovery, at the next lowest dose level.

Investigators will notify QED Therapeutics within 7 days of any DLTs observed.

**Table 7.** Criteria for defining dose-limiting toxicities

TOXICITY	DLT CRITERION
Skipped/ delayed dose	The inability to administer infigratinib on ≥ 75% of scheduled treatment days during cycle 1 at that dose (ie, ≥ 16 days of the 21 days of planned treatment) due to unresolved adverse event of any grade and considered at least possibly, probably, or definitely related to the study drug.
	Delay in 2 nd cycle administration at that dose due to failure of recovery from a possibly, probably, or definitely related adverse event to Grade ≤ 1 or baseline by Day 43 (Day 28 of Cycle 1 + 15 days), except for alopecia.
Blood/ bone marrow	Neutropenia     • Febrile, CTCAE Grade ≥ 3.     • CTCAE Grade ≥ 3 for > 7 consecutive days
	Thrombocytopenia
	Anemia CTCAE Grade 4
Renal/ genitourinary	Creatinine:  • CTCAE Grade 1 for > 7 consecutive days and serum inorganic phosphorus  > 5.5 mg/dL and/or serum total calcium x serum inorganic phosphorus  > 55 mg²/dL² and despite phosphorus lowering therapy for ≥ 14 days
	
 
CTCAE Grade 2 for > 7 consecutive days
 
CTCAE Grade ≥ 3
 

**Table 7.** Criteria for defining dose-limiting toxicities

TOXICITY	DLT CRITERION	
Hepatic	Bilirubin: • CTCAE Grade 2 for > 7 consecutive days	
	• CTCAE Grade ≥ 3	
	AST or ALT: • Grade 3 for > 7 consecutive days • CTCAE Grade 4	
	Hy's Law	
	
 
ALT or AST ≥ 3 x upper limit of normal (ULN)
 
AND
 
Serum total bilirubin > 2 x ULN
 
	
	For patients with known hepatic metastases:  • AST or ALT > 8 x ULN  OR	
	• AST or ALT > 5 x ULN for ≥ 14 days	
Pancreas	Pancreatitis CTCAE Grade ≥ 2	
	Amylase/lipase (serum-high): CTCAE Grade ≥ 3 asymptomatic amylase and/or asymptomatic lipase not reversible to CTCAE Grade ≤ 2 within 7 days	
Cardiac	QTcF interval > 500ms	
	Other cardiac CTCAE Grade ≥ 3	
Constitutional	Fatigue CTCAE Grade 3 for > 7 consecutive days	
	Fatigue CTCAE Grade 4	
Ocular/visual	Any ocular/visual toxicity CTCAE Grade ≥ 3.	
Gastrointestinal	CTCAE Grade 3 or 4 nausea/vomiting and/or diarrhea despite the use anti-emetic and anti-diarrhea therapy, respectively	
Metabolic/ laboratory	
 
Hyperphosphatemia (serum-high):
 
Serum inorganic phosphorus > 7.0 mg/dL for > 7 consecutive days despite phosphorus-lowering therapy for at least 14 days.
 
Serum inorganic phosphorus > 9.0 mg/dL, despite phosphorus-lowering therapy for at least 14 days.
 
Serum inorganic phosphorus > 10.0 mg/dL
 
Hypercalcemia (serum-high)
 
Serum calcium CTCAE Grade 2 for > 7 consecutive days.
 
Serum calcium CTCAE Grade ≥ 3.
 
	
Other	Any death not clearly due to the underlying disease or known, extraneous causes.	
	Clinical evidence for any grade (CTCAE Grade ≥ 1) of ectopic, de-novo -calcification within the soft tissue including the peri-articular spaces and vascular as well as visceral tissues (eg, kidney, lung, stomach, myocardium, etc.)	
	
 
Any other CTCAE Grade 3 or 4 non-hematological toxicity except with following exclusions:
 
• Alkaline phosphatase CTCAE Grade ≥ 3.
 
• Lymphocytopenia CTCAE Grade ≥ 3 unless considered clinically significant.
 
	

